## 13. Data Review Committees

Due to the post market status of this study a Data Monitoring Committee (DMC) will not be assembled.

The independent Contract Research Organization (CRO) Baim Institute for Clinical Research, [name], will be established as the Clinical Events Committee (CEC) prior to the first enrollment of the study. The purpose of the CEC is to provide an independent medical review and classify/adjudicate, at a minimum, all deaths and potential primary safety endpoint events for seriousness and relatedness to the study device/procedure according to definitions and processes outlined in the protocol and the CEC charter. The CEC will consist of qualified cardiologists, and cardiothoracic surgeons (including a chairperson), who are not participants in the study. Additional specialists, such as echocardiologists, may also be selected as part of the CEC.

Prior to the onset of the study, a CEC charter will be drafted to establish explicit rules outlining the minimum amount of data required and the algorithm followed in order to classify/adjudicate a study endpoint related clinical event. The charter will be approved by Medtronic and the CEC members.

All valve related deaths and potential primary safety endpoint events will be reviewed and adjudicated by the CEC. All other events will be reviewed and classified by the sponsor, by qualified internal Medtronic safety individual(s) to ensure they should not be adjudicated by the full CEC and that the events are appropriately classified by the Investigator.

CEC decisions will be documented in meeting minutes, which will be maintained in the study master file.

Additional details about the CEC will be outlined in the CEC charter.

## 14. Statistical Design and Methods

Statistical analysis will be performed by Medtronic employed statisticians or their designated representatives. A separate Statistical Analysis Plan (SAP) will be developed to further describe pre-specified statistical methods, data handling rules, and analyses that will be employed. Any deviation from the original statistical analysis plan will be reported in the final study report, along with justification for the deviation(s).

The safety and clinical performance analyses will be conducted on those subjects implanted with the Mosaic and Hancock II valves with PEEK material (As Treated population).

Additional exploratory analyses of the data may be conducted as deemed appropriate.

### 14.1. Analysis Set

#### Implanted Population

The implanted population consists of all enrolled subjects who are actually implanted with a Mosaic or Hancock II device. To be considered implanted, the subject's device disposition form must show at least one device with a final disposition of "Implanted." Time zero begins at the date of the procedure.

The safety and clinical performance analyses will be conducted on those subjects implanted with the Mosaic and Hancock II valves with PEEK material (implanted population).

Additional exploratory analyses of the data may be conducted as deemed appropriate.

## 14.2. Primary Objectives

The primary objective of the study is to characterize the freedom from valve related deaths, re-intervention of, or explants related to the Mosaic and Hancock II valves with PEEK stent material in a patient population undergoing aortic or mitral valve replacement of his/her native aortic or mitral valve, at 1 year post implant. All subjects will be followed and evaluated annually up to 3 years.

### 14.2.1. Primary Endpoints

The primary endpoints are the following events related to the Mosaic and Hancock II valves with PEEK stent material:

- valve related death
- re-intervention on the study device
- explant of the study device

### 14.2.2. Sample Size

A sample size of 89 at 1 year will provide a one-sided 95% confidence interval width of 5%, when the sample event free proportion assumed to be 97% at 1 year post implant. Considering the possible attrition rate assumed to be  $\leq 10\%$  in the first year, a minimum of 100 subjects will be implanted.

### 14.2.3. Analysis Methods

No specific hypotheses have been set for the overall analysis of freedom from deaths, re-intervention, or explant related to the Mosaic and Hancock II valves with PEEK stent material. Historical control data are provided below for qualitative comparison.

1 year Endpoint	Control Value Freedom from $\pm$ Standard Error
Valve-related Death Mosaic  Hancock II 	$98.6 \pm 0.8$ $94.6 \pm 2.4$
Valve Related Reoperation Mosaic  Hancock II 	$99.1 \pm 0.6$ $100.0 \pm 3.6$
Valve-related Explant Mosaic  Hancock II 	$99.1 \pm 0.6$ $100.0 \pm 3.6$

Mosaic Mitral Bioprostheses 16-year clinical compendium

Medtronic Hancock II Long-Term Clinical Study MVR results provided in Instructions for Use

Kaplan-Meier method will be used for the time to the first valve related death, re-intervention of the study device, or explant related to the Mosaic and Hancock II valves with PEEK stent material at 1 year after procedure. Subjects not experiencing the event through 1 year after procedure will be censored. One year is defined at time point of 365 days post procedure. The product-limit estimate of the event-free rate (or event rate), the number of subjects at risk, the number of subjects with event, the number of subjects censored, and the log-log transformed lower one-sided 95% confidence interval using the Greenwood standard error will be presented. Subjects will be censored at their last visit, or death/explant/exit.

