	and intended to be implanted with a Mosaic or Hancock II device are eligible for enrollment. Data for these subjects will be collected preoperatively, intra-operatively, at discharge or ≤ 30 days post-implant (whichever comes first), 1 year (primary endpoint), 2 years, and up to 3 years post-operatively.
Sample Size	A minimum of 100 subjects will be enrolled and implanted in the study at up to 15 sites worldwide with approximately up to 7 sites in the United States and up to 8 sites in Europe.
Eligibility Criteria	
Inclusion:
 
Subjects must meet all of the following criteria to be included in the study.
 
 
1. Subject who requires aortic or mitral valve replacement of his/her native valve with a Mosaic or Hancock II bioprosthesis with PEEK Material.
 
2. Subject is geographically stable and willing to return to the implanting site for all follow-up visits.
 
3. Subject is of legal age to provide informed consent in the country where they enroll in the study.
 
4. Subject has been adequately informed of risks and requirements of the study and is willing and able to provide informed consent for participation in the clinical study.
 
 
Exclusion:
 
Subjects who meet any of the following criteria will not qualify for participation in the study.
 
 
1. Subject requires concomitant replacement of the aortic and mitral valves.
 
2. Subject requires a replacement of a previously implanted failed prosthetic aortic or mitral valve.
 
3. Subject requires a Bentall procedure for replacement of aortic valve.
 
4. Subject presents with active endocarditis, active myocarditis, or other active systemic infection.
 
5. Subject has a non-cardiac major or progressive disease, with a life expectancy of less than 1 year. These conditions include, but are not limited to: 
 
• Child-Pugh Class C liver disease
 
• Terminal cancer
 
• End-stage lung disease.
 
 
 
6. Subject has chronic renal failure, defined as dialysis therapy or GFR<30 mL/min/1.73 m^2.
 
7. Subject has hyperparathyroidism.
 
8. Subject is participating in another investigational device or drug study or observational competitive study.
 

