## **10.10. Subject Withdrawal or Discontinuation**

It is the subject's right to withdraw at any time from the study and for any reason without sanction, penalty or loss of benefits to which the subject is otherwise entitled, and without jeopardizing their future medical care. The Investigator may withdraw the subject at any time to protect the health, safety or welfare of the subject. At the last point of contact (if outside a study-required visit), every effort should be made to collect the status of any ongoing adverse events.

The subject may only be considered lost to follow-up after all efforts to obtain compliance are exhausted. At a minimum, four attempts must be made to contact the subject and documented in the subject's study records:

- 3 telephone attempts to the subject's last known phone number, and if unsuccessful,
- 1 certified letter from the PI to the subject's last known address

If the site is unable to reach the subject after the documented attempts, the site should make every attempt to verify the subject's vital status (alive or deceased).

All subjects will be encouraged to remain in the study through the last follow-up visit. Subjects who discontinue participation prematurely will be included in the analysis of results. If the subject discontinues participating in the study prior to completing the study requirements, the reason for withdrawal will be recorded in the subject's study records and on the appropriate eCRF.

Subject's enrolled in the study but do not receive the study device may be replaced in the study as long as the replacement does not go beyond the 22 subjects implanted at that site or the 110 study subject maximum.

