**Table 6. Study Exit Scenarios**

Scenario	Follow-up Required	eCRFs Required
Subject enrolled (informed consent signed), but the study device never contacts subject, and no Mosaic or Hancock II valve with PEEK material is implanted	None	-Inclusion/Exclusion eCRF -Baseline eCRF (as applicable) -Study Exit eCRF
Subject enrolled, the study device comes into contact with the subject (i.e. passes the body plane) but no Mosaic or Hancock II valve with PEEK material is implanted	30 days post-attempted implant for safety only	-Eligibility eCRF -Baseline eCRF (including labs/echo) -Implant eCRF -AE/DD eCRF (as appropriate) -Study Exit eCRF
Subject enrolled, implanted with Mosaic or Hancock II valves with PEEK material, and exits the study early due to explant	Through the point of explant/study exit.	-All required/ unscheduled eCRFs through last visit completed -Valve Reintervention eCRF -AE/DD eCRF (as applicable) -Study Exit eCRF
Subject enrolled, implanted with Mosaic or Hancock II valves with PEEK material, and exits the study early due to any of the following:  - Lost to Follow-up - Death - Withdrawal	Through point of death, withdrawal, or last visit completed	-All required/ unscheduled eCRFs through last visit completed -AE/DD eCRF (as applicable) -Study Exit eCRF
Subject enrolled, implanted and completes the study requirements	Through 3 year follow-up	-All required/ unscheduled eCRFs -AE/DD eCRF (as appropriate) -Study Exit eCRF

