7.4. Handling of Missing Data and Dropouts

Unless specified otherwise in each objective, no statistical techniques will be used to impute missing data. If a subject's data are missing for any reason, that subject will not be included in that portion of the analysis. The number of subjects included in each analysis will be reported so that the potential impact of missing data can be assessed.

In the case of partial dates, the general rule is as follows:

- If only the month and year are known, the event or assessment will be analyzed as if it occurred on the 15th of that month.
- If only the year is known, the event or assessment will be analyzed as if it occurred on June 30th of that year.

These resolutions of partial dates are subject to the restrictions that pre-procedure events and assessments must occur between the enrollment date and the procedure date, and post-procedure events and assessments must occur no earlier than the procedure date. If additional information about the partial dates might be known, for example, the event occurs after 15th of the month, then data may be analyzed as if it occurred on the 16th of the month.

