7.6.1.3. Data Collection and Analysis Methods

Death, re-intervention, or explant related to the Mosaic and Hancock II valves will be adjudicated by the Clinical Events Committee (CEC) and collected on the CEC form. CEC adjudication shall overwrite the Medtronic classification of the events or site classification of the events.

Kaplan-Meier method will be used for time to the first valve related death, re-intervention of, or explant of the study valve related to the Mosaic and Hancock II valves with PEEK stent material at 1 year after procedure. Subjects not experiencing the event through 1 year after procedure will be censored. One year is defined at timepoint of 365 days post procedure. The product-limit estimate of the event-free rate (or event rate), the number of subjects at risk, the number of subjects with event, the number of subjects censored, and the log-log transformed lower one-sided 95% confidence interval using the Greenwood standard error will be presented.

Specifically, Kaplan-Meier estimate is as follows.

$$\hat{S}(t_k) = \prod_{j=1}^k \left(1 - \frac{d_j}{n_j}\right)$$

Greenwood variance is estimated as below.

$$Var(\hat{S}(t_k)) = \hat{S}(t_k)^2 \sum_{j=1}^k \frac{d_j}{n_j(n_j - d_j)}$$

Pointwise one-sided lower 95% confidence interval at 365 days post procedure after log-log transformation (Kalbfleisch and Prentice; 1980) is as below.

$$\hat{S}(t)^{\exp(z_{\alpha} * tao)}$$

$$\text{where } tao = \frac{\sigma(\hat{S}(t))}{\hat{S}(t) * \log(\hat{S}(t))}$$

A Kaplan-Meier plot will also be presented.

This objective will be analyzed for the implanted population.

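### The last sentence of protocol 14.2.3 would censor primary events as written, and neither document fixes the censoring date for losses before day 365

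*Protocol*

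**What the plan says.** Protocol 14.2.1 lists three primary events: valve-related death, reintervention, and "explant of the study device". Protocol 18.5.2.2 defines explant as removal for any reason after the index procedure, and 10.3.8.3 treats every reintervention as prosthesis-related.

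Protocol 14.2.3 analyses time to the first of these events by Kaplan-Meier at day 365. It censors subjects without an event, and then ends with "Subjects will be censored at their last visit, or death/explant/exit".

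Protocol 14 leaves a separate SAP "to further describe pre-specified statistical methods, data handling rules, and analyses that will be employed". SAP 7.6.1.3 omits the closing sentence. It says "Subjects not experiencing the event through 1 year after procedure will be censored" and sets 1 year at day 365, but gives no date for a subject lost earlier.

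Three other places bear on the date:
- Protocol Table 6 sets follow-up for subjects who die, withdraw or are lost as "Through point of death, withdrawal, or last visit completed", and has a separate row ending follow-up at explant.
- Protocol 10.10 says "Subjects who discontinue participation prematurely will be included in the analysis of results".
- SAP 7.4 says "If a subject's data are missing for any reason, that subject will not be included in that portion of the analysis".

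After discharge (day 30 at the latest), the Synopsis schedules data collection at "1 year (primary endpoint), 2 years, and up to 3 years post-operatively". The 1-year window in 10.3.10 is 365 ± 30 days, so it opens at day 335.

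**The concern.** Two things are wrong with the closing sentence.

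**It censors outcomes that are events.** For explant the conflict is complete: every post-index explant is an event, so none can properly be a censoring. For death, a qualifier is missing: censoring is right for a death that is not valve-related, and the sentence does not say so.

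**It names several dates without ranking them.** A subject who withdraws on day 200 after a discharge visit on day 10 could be censored on either day. With no visit scheduled between discharge and 1 year, last visit can take most of a year of observation away from such a subject. In the interim report due when all 1-year visits are done (protocol 10.6 and 10.7), last visit would also censor an event-free subject seen on days 335 to 364 before the analysis time point.

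At stake is the study's only primary estimate, its one-sided lower bound, and the numbers at risk and censored that both documents plan to report. Two programmers could produce different figures and each cite the text.

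**Working it through.** **Planning figure.** SAP 6 gives n = 89 for a one-sided 95% Clopper-Pearson width of at most 5% at 97% event-free. With x = 0.97n left unrounded, the width is 0.0501 at n = 88 and 0.0497 at n = 89, so 89 reproduces. At 10% attrition, 89/0.90 = 98.9, consistent with the minimum of 100 implanted. The censoring question changes neither figure.

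**Method for the illustrations** (SAP 7.6.1.3). S is the product of (1 − d/n) over event times. V is the Greenwood sum of d/[n(n − d)]. tao = √V / ln S. The lower bound is S^exp(−1.645 × tao), where tao is negative. Inputs from the documents: 100 implanted and 97% event-free, hence 3 events. The timing of events, losses and visits is assumed; neither document gives it.

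**1. One event wrongly censored.** No losses; events on days 90, 180 and 270.
- All counted: S = (99/100)(98/99)(97/98) = 0.9700; V = 0.000309; tao = −0.577; bound = 0.97^2.585 = 92.4%.
- Third one censored: S = (99/100)(98/99) = 0.9800; V = 0.000204; tao = −0.707; bound = 0.98^3.200 = 93.7%.

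The estimate rises by 1.0 point and the bound by 1.3. One of three is an arbitrary choice. The shift grows with the share of events that are deaths or explants; if all three were and all were censored, the estimate would be 100% and the log-log bound undefined.

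**2. Date of loss.** Ten losses (10% of 100); events on days 90, 180 and 270.

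| Losses dated at | At risk at the three events | Estimate | Lower bound |
|---|---|---|---|
| Exit, spread over days 20–345 | 98, 94, 91 | 96.85% | 92.06% |
| Discharge, all ten | 90, 89, 88 | 96.67% | 91.61% |
| Discharge five, exit five | 94, 91, 89 or 94, 92, 90 | 96.75% or 96.77% | 91.81% or 91.87% |

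The bound moves by 0.45 point at most, and by about 0.2 if half the losses are affected.

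**3. Completers in the interim report.** 100 − 3 − 10 = 87 completers, visits spread evenly over days 335–395, and no year-2 visit yet done. Censored at the visit, 44 remain at risk at day 365 instead of 87. The third event is moved as shown.

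| Third event on day | At risk then: visit rule vs full follow-up | Lower bound: visit rule vs full follow-up |
|---|---|---|
| 270 | 91 vs 91 | 92.06% vs 92.06% |
| 340 | 81 vs 89 | 91.71% vs 92.00% |
| 350 | 66 vs 88 | 90.92% vs 91.96% |
| 360 | 52 vs 88 | 89.65% vs 91.96% |

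Some early implants will already have a year-2 visit. With even enrolment over 15 months (protocol 7.1), the first subject is 15 + 12 = 27 months out when the last reaches 12, so (27 − 24)/15 = 20% have passed 24 months. If that share applies to the 43 seen before day 365, about 9 return to the risk set: roughly 53 of 87 rather than 44.

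**The case against.** The strongest reply is that the intent is clear. The same paragraph of 14.2.3 already limits censoring to subjects without the event and analyses time to the first event, and the SAP repeats that limit while leaving the loose sentence out. The closing sentence resembles Table 6, which lists when follow-up ends and largely supplies the dates: death, withdrawal or explant at that point, and loss to follow-up at the last completed visit. Most of this stands, and it makes the problem a drafting error rather than a flawed design. It does not make the sentence correct, and Table 6 is a follow-up table that the SAP never cites as a censoring rule.

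A reader might draw four stronger conclusions that the documents do not support:

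- *The plan intends to discard primary events.* The rest of 14.2.3 and SAP 7.6.1.3 point the other way.
- *SAP 7.4 drops early losses from the primary analysis, against protocol 10.10.* That is strained. A censored subject has a valid time-to-event record, and the number censored is a planned output.
- *It is open whether only device-related explants and reinterventions count.* Protocol 10.3.8.3 and 18.5.2.2 largely settle this, and protocol 13 has the events committee work to the protocol's definitions.
- *Half the subjects vanish from the risk set, so the requirement for 89 followed to 1 year fails.* The drop mainly concerns the interim report. In the final report, which SAP 3 names as its scope, the last visit of a retained subject is at year 2 or 3. Protocol 7.1 also asks for subjects followed, not for a Kaplan-Meier number at risk.

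**Conclusion.** The closing sentence of 14.2.3 is wrong as written, and the censoring date for losses before day 365 is not fixed in either document. The consequences are modest. There is no hypothesis or success threshold, and the comparison with historical data is qualitative. The literal reading would matter most: about 1.0 point on the estimate and 1.3 on the bound for each wrongly censored event of three, always in the device's favour. The choice of date for 10 losses is worth 0.5 point on the bound or less. The interim effect is on the reported number at risk; the bound is unchanged unless an event falls after day 335, and it reached 2.3 points only with an event placed on day 360. All these sizes rest on assumed timing. The case for acting is that the text can produce two different primary results and the remedy is cheap.

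**What to change.** Replace the closing sentence of protocol 14.2.3 and put the same text in SAP 7.6.1.3, for example:

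> A valve-related death, a reintervention on the study valve or its removal counts as an event on the day it happens and is not censored. A subject without an event is censored at the earliest of day 365, a death that is not valve-related, and the last day on which the subject is documented to be event-free (scheduled or unscheduled visit, telephone or other documented contact, or withdrawal made with contact). The adjudicated date of a death that is not valve-related counts as a documented date. For a subject lost to follow-up, the date is the last documented contact, not the administrative exit date.

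The last clause is needed because, under protocol 10.10, loss to follow-up is declared only after failed calls and a letter, so the exit date says nothing about event status. Add one sentence to the SAP saying that early discontinuers stay in this analysis as censored subjects and that the exclusion in 7.4 does not apply to them.

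The cost is a text change in each document, with no extra patients or visits. The one practical burden falls on the interim report: subjects seen before day 365 need a documented status on or after that day, or they stay censored at their visit.

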## 7.1. Duration

Enrollment is estimated to take approximately 15 months to complete, and subjects will consent to be followed annually up to 3 years post procedure. A minimum of 89 subjects is required to be followed to 1 year to satisfy the primary endpoint requirements: freedom from valve related death, re-intervention of, or explant related to the Mosaic and Hancock II valves with PEEK stent material. Total expected duration of the study is approximately 5 years. The study will be considered complete when the last active implanted subject completes the 3 year required follow-up.

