#### **10.3.10. 1 Year (365 $\pm$ 30 days) Post-Procedure Follow-up Assessment**

Subjects will be seen at 1 year ( $\pm$  30 days) post-procedure. The following evaluations will be completed and data recorded on the appropriate eCRFs:

- NYHA classification
- 12 lead ECG
- Hematology/chemistry data
- Transthoracic Echocardiography (TTE)
- Relevant medications
- Adverse events/device deficiency

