**10.3.11. Annual Year 2 (730 ± 60 days) Post-Procedure Follow-up Assessment**

Subjects will be seen at 2 years (730 ± 60 days) post-procedure. The following evaluations will be completed and data collected on the appropriate eCRFs:

- NYHA classification
- 12 lead ECG
- Hematology/chemistry data
- Transthoracic Echocardiography (TTE)
- Relevant medications
- Adverse events/device deficiency

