### **10.7. Assessment of Safety**

An Interim report on the study will be conducted at the completion of all subject's 1 year follow-up visit. The primary endpoint will be used to measure the safety of the study device. Primary endpoint adverse events of valve related death, and reintervention of, or explant related to the Mosaic and Hancock II valves with PEEK stent material will be regularly reviewed by an independent CEC. All device and therapy related adverse events will be collected throughout the study.

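### Censoring at the last visit, with a 1-year visit allowed from day 335, can take event-free subjects out of the day-365 risk set in the 1-year report; the SAP does not contain this rule

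*Protocol*

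**What the plan says.** Protocol 14.2.3 sets the time point: "One year is defined at time point of 365 days post procedure". It then gives two statements about censoring. The first is "Subjects not experiencing the event through 1 year after procedure will be censored", which can be read as censoring at day 365. The second, at the end of the paragraph, is "Subjects will be censored at their last visit, or death/explant/exit".

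SAP 7.6.1.3 repeats the day-365 Kaplan-Meier analysis and the first statement but not the second.

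Four other places bear on the point:
- Protocol 10.3.10 sets the 1-year visit at 365 ± 30 days, so days 335 to 395. The year-2 visit (10.3.11) is at 730 ± 60 days, so days 670 to 790.
- Protocol 10.7 times the first report: "An Interim report on the study will be conducted at the completion of all subject's 1 year follow-up visit". Section 10.6 says the same.
- Protocol 12.1.2 keeps reportable events coming in from enrollment until subject exit, whatever the visit dates.
- Protocol 7.1 states: "A minimum of 89 subjects is required to be followed to 1 year to satisfy the primary endpoint requirements". Neither document says whether a subject seen on day 340 counts toward that number.

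**The concern.** When the 1-year report is run, the 1-year visit is the most recent visit for most subjects. Under the last-visit rule, an event-free subject seen on day 340 is censored on day 340. A similar subject seen on day 340 who has a reintervention on day 355 is still counted as an event on day 355. Leaving the risk set between days 335 and 364 thus depends on the visit date for event-free subjects only. The denominator shrinks just before the time point while the numerator does not, which pushes the estimate down and weakens its precision.

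There is also a question of reproducibility. One programmer following the SAP and another following the last sentence of Protocol 14.2.3 could obtain different primary results from the same data.

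**Working it through.** **The plan's own figure.** The sample size (Protocol 14.2.2, SAP 6) assumes 97% event free and a one-sided 95% Clopper-Pearson limit, with a width of 5% or less. The lower limit is the 5% quantile of Beta(0.97n, n − 0.97n + 1). At n = 88 the width is 0.0501 and at n = 89 it is 0.0497, so 89 is reproduced. Then 89/0.9 = 98.9, consistent with 100 implants at 10% attrition.

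**Number at risk at day 365.** Inputs from the documents are N = 100 implanted, attrition a = 10%, 97% event free, and a window of days 335 to 395 (61 days). Two inputs are assumptions: visits spread evenly over the window, and uniform accrual over the 15 months in Protocol 7.1.

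At risk = N × (1 − a) × 0.97 × [y + (1 − y) × p]

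Here p is the share of 1-year visits on or after day 365, 31/61 = 0.508. The share with a year-2 visit already made when the report is run is y.

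- Status known to day 365: 100 × 0.9 × 0.97 = 87.3.
- Last visit, y = 0: 87.3 × 0.508 = 44.4.
- Last visit, y = 0.22 (simulated with 15-month uniform accrual and a data cut at the last 1-year visit): 87.3 × (0.22 + 0.78 × 0.508) = 87.3 × 0.616 = 53.8.

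Other visit timings, simulated with 100 implants and 10% attrition:

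| Visit timing | y = 0 | year-2 visits counted |
|---|---|---|
| Leaning early | 28 | 40 |
| Even | 44 | 54 |
| Leaning late | 61 | 67 |
| All on day 335 (extreme) | 0 | 11 |
| All on day 365 (extreme) | 87 | 87 |

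With the SAP's attrition of up to 20% and even visits, the figures are 39 and 47, against about 78 with status known.

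**Average effect.** Simulated trials with 100 implants, 10% loss, even visits and a constant hazard giving 97% at day 365 put the estimate 0.07 to 0.09 point lower under last-visit censoring. The mean width is about 0.12 to 0.16 point greater, from a base of about 4.8 points. If most events come early, both changes are smaller.

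**One late event.** Take three events, the first two with 99 and 97 at risk and the third shortly before day 365 with m at risk. Then:

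- S = (98/99) × (96/97) × (1 − 1/m)
- G = 1/(99×98) + 1/(97×96) + 1/(m(m − 1))
- lower limit = S^k, with k = exp(1.645 × √G / |ln S|)

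| m | S | k | Lower limit |
|---|---|---|---|
| 89 | 96.9% | 2.59 | 92.1% |
| 54 | 96.2% | 2.70 | 90.0% |
| 48 | 95.9% | 2.75 | 89.2% |

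The censoring rule alone costs 92.1 − 90.0 = 2.1 to 92.1 − 89.2 = 2.9 points on the limit. With even visits and y = 0, a risk set of 48 is reached at about day 362 (87.3 × 34/61 = 48.7).

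**How often.** With 3% events at a constant rate, about 3 × 30/365 = 0.25 events per 100 subjects fall in the 30 days before day 365. The chance of at least one is about 1 − exp(−0.25) = 22%.

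**The case against.** A reader might infer three stronger conclusions that the documents do not support.

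- *Fewer than half of subjects will be at risk at day 365.* This needs visits that are even or early and almost no year-2 visits by the time of the report. The documents give no visit distribution, and 15-month accrual means roughly a fifth of subjects would already have had a year-2 visit. Even visits then leave about 54 of 100, and late-leaning visits 61 to 67.
- *The requirement of 89 is breached.* The 89 is the denominator of a single proportion and includes subjects with events. A Kaplan-Meier risk set excludes them. Even with complete status only about 87 of 100 are at risk at day 365, so the number at risk is the wrong quantity to hold against 89. The protocol asks for subjects followed to 1 year without defining the term, and a completed 1-year visit may be what is meant.
- *The interval will be wider than planned.* On average it stays at or just under 5 points at 10% attrition.

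It is also fair that no hypothesis or performance goal is set, that comparison with historical values is qualitative, and that the last-visit sentence may have been meant only for subjects who leave early. By the final report, anyone with a year-2 or year-3 visit has a last visit after day 365, so the problem mostly vanishes. Serious events are reported promptly between visits, and the number at risk is already to be presented.

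All of this limits the size of the point. What stands is that the sentence as written censors event-free subjects before the time point in the 1-year report, that the SAP does not contain it, and that the result is exposed to a late event.

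**Conclusion.** The concern holds in a limited form. In the 1-year report, the last-visit rule together with a window opening at day 335 can leave only about 45 to 55 of 100 subjects at risk at day 365 if visits are evenly spread, and about 28 to 67 for visits leaning early or late. About 87 would be at risk with status known. The average bias is under 0.1 point and the average loss of precision 0.1 to 0.2 point, neither of which would change a reading of the study. The material exposure is an event shortly before day 365, which can lower the limit by 2 to 3 points in a study sized around a 5-point width.

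These sizes rest on assumed visit timing, uniform accrual, 10% attrition and a constant hazard. The disagreement between protocol and SAP on when to censor rests on no assumption. The point is worth correcting before the 1-year report but does not threaten the final result.

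**What to change.** - **One censoring rule in both documents.** Censor event-free subjects at the last date they are known to be event free from any visit, contact or record, and administratively at day 365 for the 1-year estimate.
- **Status check before the 1-year report.** For subjects whose 1-year visit fell on days 335 to 364, confirm event status on or after day 365 by chart or phone. Protocol 10.4.1 already expects contact about vital status and adverse events when a visit is missed, so this is a modest extension.
- **Define being followed to 1 year.** Use: event status known to day 365, or a primary event before it. Count that number against the 89. With 100 implants and 10% loss it is about 90 (87 event free plus about 3 with events). Continue to present the Kaplan-Meier number at risk, but do not compare it with 89.

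The cost is an edit to the protocol and SAP, a short status check for up to about half of subjects (30/61 = 49% with even visits), and possibly a delay of up to 30 days for the last of them.
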